#### **10.3.1 Temporary treatment discontinuation with investigational medicinal product**

Temporary treatment discontinuation may be considered by the Investigator because of suspected AEs.

Lower extremity complications (such as skin ulcers, infection, osteomyelitis, and gangrene) requiring treatment should lead to temporary discontinuation of IMP.

If at any visit after Randomization up to Week 8 there is a rise in creatinine level (ie, >50% increase from Baseline level, where Baseline level is defined as the mean of creatinine values obtained at Screening and Randomization) or if at any visit after Week 8 there is a rise of >50% above the mean of creatinine values from last 2 visits, the Investigator should ensure that no reasonable explanation exists for creatinine increase.

The IMP should be stopped for 2 weeks.

Reinitiating of treatment with the IMP will be done under close and appropriate clinical/and or laboratory monitoring once the Investigator has considered according to his/her best medical judgment in the occurrence of the concerned event was unlikely to be related to the IMP and if that the selection criteria for the study are still met (refer to [Section 7.1](#) and [Section 7.2](#)).

If at creatinine recheck the patient has returned to the below threshold then IMP will be restarted at a reduced dose (ie, dose reduced via IRT to 200 mg for those randomized to 400 mg; maintained at 200 mg for those randomized to 200 mg). Since the IMP received is blinded, patients must return to the site and IRT will be contacted for IMP re-initiation.

It is in the interest of the patient to monitor their blood glucose during the temporary discontinuation period, therefore regular determination of SMBG is to be performed and documented (see [Section 9.2.1.8](#)).

For all temporary treatment discontinuations, duration should be recorded by the Investigator in the appropriate pages of the e-CRF when considered as confirmed.

Temporary treatment discontinuation decided by the Investigator corresponds to more than 1 dose not administered to the patient.

Use of any other anti-hyperglycemic medication during the time of temporary treatment discontinuation (ie, insulin during a hospitalization) is to be recorded as concomitant medication with the name and dose recorded in the e-CRF.

### **10.3.2 Permanent treatment discontinuation with investigational medicinal product**

Permanent treatment discontinuation defined as any treatment discontinuation associated with the definitive decision from the Investigator or the patient not to re-expose the patient to the IMP at any time.

#### **10.3.3 List of criteria for permanent treatment discontinuation**

Patients may withdraw from treatment with the IMP if they decide to do so, at any time and irrespective of the reason, or this may be the Investigator's decision. Patients should discuss stopping study medication with the site before doing so in order that questions can be addressed, glycemic therapy adjusted, and a follow-up assessment arranged. All efforts should be made to document the reasons for treatment discontinuation; this reason should be documented in the e-CRF.

The following reasons can lead to permanent discontinuation:

- At the patient's own request (ie, withdrawal of consent for treatment).
- If, in the Investigator's opinion, continuation with the administration of the study treatment would be detrimental to the patient's well-being.
- Intercurrent condition that requires permanent discontinuation of the study treatment as long as the abnormality persists and if the casual relationship of the concerned event and the IMP is possible (according to the Investigator's best medical judgment).
- Deterioration of renal function (defined as increase in serum creatinine > 50% from Baseline) that is not recovered after a temporary IMP discontinuation for 2 weeks.
- Patient requires renal replacement therapy (transplant or dialysis).
- Pregnancy (in female patients).
- Specific request of the Sponsor.

Any abnormal laboratory value will be rechecked immediately to confirm the result before a decision is made to permanent discontinue IMP for the concerned patient.

For patients who prematurely discontinue the IMP, the assessments planned at EOT visit ([Section 10.1.3.2](#)) will be performed at the Premature EOT Visit scheduled preferably prior to treatment discontinuation or as soon as possible after the time of discontinuation (at the latest at the next scheduled on-site visit). In the case of premature IMP discontinuation, no sample for measuring plasma concentration should be taken at the Premature EOT Visit, or at any subsequent

visit. The reason(s) for IMP discontinuation will be clearly specified. This Premature EOT assessment may occur at a regularly scheduled or at an unscheduled visit.

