	
when reaching the target number as planned.
 
Following randomization, patients will have a 26-week double-blind Treatment Period, followed by a 26-week double-blind Extension Period, and a 4-week post-treatment Follow-up Visit to collect safety and some efficacy information.
 
Patients will be monitored throughout the double-blind Treatment Period and Extension Period for signs of deterioration in renal function (eg, decrease in eGFR) as well as all other routine clinical and laboratory findings. If at any visit after Randomization up to Week 8 there is a rise in creatinine level (ie, >50% increase from Baseline level, where Baseline level is defined as the mean of creatinine values obtained at Screening and Randomization) or if at any visit after Week 8 there is a rise of >50% above the mean of creatinine values from the previous 2 visits, the Investigator should ensure that no reasonable explanation exists for creatinine increase and in particular the following causes:
 

• Medications that increase creatinine

• Decrease in cardiac output

• Obstructive uropathy

• Urinary tract infection

• Volume depletion.

 
If addressing these causes does not reduce the creatinine level below the above stated threshold, the investigational medicinal product (IMP) will be stopped for 2 weeks. If at creatinine recheck the patient has returned to the below threshold, then IMP will be restarted at a reduced dose (ie, dose reduced via interactive response technology to 200 mg for those randomized to 400 mg, maintained to 200 mg for those randomized to 200 mg, and to placebo for those randomized to placebo). If the creatinine does not return to below the threshold, the IMP will be permanently discontinued but the patient will be asked to continue attending all study visits.
 
The HbA1c and FPG results will be masked to study sites and patients after randomization and until study end. To prevent partial unblinding, UGE and UGCR results will also be masked to study sites and patients. Additionally, urinalysis by dipstick will not include the measurement of urine glucose.
 
Quantitative urine glucose, albumin, calcium, phosphorus, magnesium, and creatinine will be measured separately at all on-site visits by the central laboratory.
 
Early termination
 
If a patient discontinues treatment with IMP early during the Treatment Period, the patient will have a Premature End of Treatment (EOT) visit and a Follow-up Visit 4 weeks after the last dose of IMP. In addition, every effort will be made to have all patients return to the site at the time corresponding to their scheduled visits, particularly the Week 26 and Week 52 visits.
 
If a patient does not agree to site visits, he/she will be contacted by telephone to enquire about their safety information, particularly at the time of the initially scheduled end of study.

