#### 8.1.1 Dose reduction

The dose maintenance will be handled according to the renal function assessed by the creatinine measurement throughout the study. If at any visit after Randomization there is a rise in creatinine level (see details in Section 10.6.2), the Investigator should ensure that no reasonable explanation exists for creatinine increase. Sites will be notified by central laboratory alert if a patient has a >50% increase from Baseline level or >50% above the mean of creatinine values from the last

2 visits, where Baseline level is defined as the mean of creatinine values obtained at Screening and Randomization. The IMP should be stopped for 2 weeks. If at creatinine recheck the patient has returned to the below threshold then IMP will be restarted at a reduced dose (ie, dose reduced via IRT to 200 mg for patients randomized to 400 mg, maintained to 200 mg for patients randomized to 200 mg, and to placebo for patients randomized to placebo). Since IMP received is blinded, patients must return to the site and IRT will be contacted for this IMP re-initiation. Dose reduction can only be obtained at on-site visit by IRT. If the creatinine does not return to below the threshold, the IMP will be permanently discontinued but the patient will be asked to continue attending all study visits.

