## **10.6.2 Deterioration of renal function**

Patients will be monitored throughout the double-blind Treatment Period and Extension Period for signs of deterioration in renal function (eg, decrease in eGFR or increase in creatinine as defined below) as well as other routine clinical and laboratory findings (see Study Flowchart, [Section 1.2](#)). If at any visit after Randomization up to Week 8 there is a rise in creatinine level (ie,  $> 50\%$  increase from Baseline level, where Baseline level is defined as the mean of creatinine values obtained at Screening and Randomization) or if at any visit after Week 8 there is a rise of  $> 50\%$  above the mean of creatinine values from last 2 visits, the Investigator should ensure that no reasonable explanation exists for creatinine increase and in particular the following causes:

- Medications that increase creatinine
- Decrease in cardiac output
- Obstructive uropathy
- Urinary tract infection
- Volume depletion.

If addressing these causes does not reduce the creatinine level below the above stated threshold, the IMP will be stopped for 2 weeks. The dose will be handled according to the renal function assessed by the creatinine measurement throughout the study and as detailed in [Section 10.3.1](#).

If the creatinine dose not return to below the threshold, then the IMP will be permanently discontinued but the patient will be asked to continue attending all study visits

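### Protocol 10.3.3 measures the renal reason for permanent stop against Baseline throughout, while the mandatory rule in 10.6.2 switches after Week 8 to the mean of the last two visits

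*Protocol*

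**What the plan says.** The mandatory rule is stated consistently. The synopsis, 10.3.1, 10.6.2 and footnote t of the flow chart (1.2) all set the trigger at a creatinine rise of more than 50%. Up to Week 8 the reference is Baseline. After Week 8 the rise must be "above the mean of creatinine values from last 2 visits" (10.6.2).

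After a 2-week interruption there are two outcomes. On restart, the synopsis says: "If at creatinine recheck the patient has returned to the below threshold, then IMP will be restarted at a reduced dose". On stopping, it says: "If the creatinine does not return to below the threshold, the IMP will be permanently discontinued". Sections 8.1.1 and 10.6.2 make the same stop mandatory.

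Section 10.3.1 adds conditions to any restart: the Investigator must judge the event unlikely to be related to IMP, and the selection criteria must still be met.

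Section 10.3.3 lists criteria for permanent discontinuation under the introduction "The following reasons can lead to permanent discontinuation". Its renal bullet defines deterioration as serum creatinine more than 50% "from Baseline) that is not recovered after a temporary IMP discontinuation for 2 weeks". It mentions neither Week 8 nor recent visits, does not refer to 10.6.2, and does not say what level counts as recovery. The same list has a separate reason based on the Investigator's opinion.

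**The concern.** Creatinine controls dosing in this CKD 3A/3B trial. It decides between restart at a reduced dose and a permanent stop. Section 10.3.3 is where a site would naturally look up the permanent-stop criteria, and after Week 8 its reference differs from the one that governs the mandatory decision. A site relying on 10.3.3 could miss a required stop, or could treat a patient who qualifies for restart as a permanent stop. The reason for discontinuation is also recorded in the e-CRF and tabulated (Protocol 11.2, SAP 2.2). A patient stopped under 10.6.2 may not fit the renal reason as 10.3.3 words it.

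**Working it through.** The plan gives no figure to reproduce. The check compares the two limits and then applies them to illustrative values.

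**Limits after Week 8.** Let B be Baseline creatinine and M the mean of the two visits before the trigger. The 10.6.2 limit is 1.5 × M and the 10.3.3 limit is 1.5 × B. They agree only when M = B. A recheck between them is classified differently.

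**Assumptions.** The creatinine values are invented. The recheck is judged against the same M that triggered the interruption. The patient is a non-Black man aged 65. SAP 2.5.1 gives eGFR = 175 × Cr^-1.154 × age^-0.203, and 175 × 65^-0.203 = 74.99. Both Baselines used below are eligible (30 to <60): 1.25 mg/dL gives 57.97 and 1.50 mg/dL gives 46.97.

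**Recent mean below Baseline.** B = 1.50; last two visits 1.28 and 1.32; trigger 2.15; recheck 2.10 mg/dL.
- M = (1.28 + 1.32)/2 = 1.30, so the 10.6.2 limit is 1.5 × 1.30 = 1.95.
- The trigger is 2.15/1.30 = 1.654, a rise of 65%. The recheck is 2.10/1.30 = 1.615, still 62% above M. Section 10.6.2 requires a permanent stop.
- The 10.3.3 limit is 1.5 × 1.50 = 2.25. Trigger and recheck are 2.15/1.50 = 1.433 and 2.10/1.50 = 1.400, so the 10.3.3 definition is never met, however recovery is read.
- The omitted band is 1.95 to 2.25 mg/dL, a width of 0.30.

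**Recent mean above Baseline.** B = 1.25; last two visits 1.45 and 1.55; trigger 2.30; recheck 2.00 mg/dL.
- M = (1.45 + 1.55)/2 = 1.50, so the 10.6.2 limit is 2.25. The trigger is 2.30/1.50 = 1.533. The recheck is 2.00/1.50 = 1.333, which is below the limit, so the restart rule applies.
- The 10.3.3 limit is 1.5 × 1.25 = 1.875. The recheck is 2.00/1.25 = 1.600, still 60% above Baseline. The bullet supports a stop if not recovered means still more than 50% above Baseline.

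**Effect of the 10.3.1 restart condition.** The selection criteria include eGFR of at least 30 (I 01) and exclude CKD stage 4 (E 21).
- At 1.5 × B, eGFR is multiplied by 1.5^-1.154 = 0.626. Staying at or above 30 therefore needs Baseline eGFR of at least 30/0.626 = 47.9. A patient with Baseline eGFR of 45 would fall to 45 × 0.626 = 28.2 and would not qualify for restart.
- For the example patient, eGFR reaches 30 at creatinine (74.99/30)^(1/1.154) = 2.21 mg/dL. The conflicting band is therefore 1.875 to 2.21 mg/dL (width about 0.34), not 1.875 to 2.25.
- The recheck of 2.00 gives 74.99 × 2.00^-1.154 = 33.7, so this example survives the condition.

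**The case against.** The strongest reply is that 10.3.3 only says what can lead to a stop. It is not stated to be exhaustive and it prohibits nothing. The mandatory stop appears three times elsewhere, and a site that obeys it breaches nothing in 10.3.3. This stands. A reader might infer that the two sections give opposite instructions in both directions, but the documents do not support that. When the recent mean is below Baseline, the bullet is silent about a required stop and does not countermand it.

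The reply for the other direction is that it depends on one reading of recovery. The words could equally refer back to the interruption procedure in 10.3.1 and 10.6.2, and 10.3.1 limits restart further. Both points stand as limits. The selection-criteria condition closes the conflict for patients with Baseline eGFR below about 48. It does not remove it for the rest, and the Investigator's judgement of relatedness to IMP sets no creatinine reference.

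A reader might also infer that 8.1.1 is defective, because its alert sentence ("Sites will be notified by central laboratory alert if a patient has a >50% increase from Baseline level or >50% above the mean of" recent values) names both references without the Week 8 split. That does not hold: 8.1.1 already points to 10.6.2 for the details, and footnote t states the split.

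**Conclusion.** The concern holds in a limited form. One safety threshold is worded two ways, and the 10.3.3 bullet is the outlier. After Week 8 the bullet leaves out a mandatory stop when the recent mean is below Baseline. When the recent mean is above Baseline it can support a stop against the restart rule. This second case needs recovery to be read against Baseline and the patient still to be eligible at restart, in practice with Baseline eGFR above about 48 mL/min/1.73 m².

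The size is illustrative: bands of 0.30 and about 0.34 mg/dL in invented creatinine paths, assuming the recheck is compared with the triggering mean. The documents give no frequency.

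A reader might infer a consequence for alpha, power or the primary estimate. Nothing in the documents supports one. The sample size and testing order do not use the creatinine rule, and the primary analysis keeps HbA1c measured after IMP discontinuation. This is a minor cross-section correction.

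**What to change.** Reword the renal bullet in 10.3.3 along these lines: *creatinine not returned below the applicable Section 10.6.2 threshold at recheck after a 2-week IMP interruption*. Discretionary stops in patients still well above Baseline remain covered by the Investigator's-opinion reason in the same list. The 10.6.2 thresholds, the restart rule and 8.1.1 need no change. The cost is one bullet of protocol wording, with no new visits, samples, stopping rules or analyses.

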#### **10.3.4 Handling of patients after permanent treatment discontinuation**

Every effort should be made to maintain patients in the study. Patients should be followed up according to the study procedures as specified in this protocol up to the scheduled date of study completion, or up to recovery or stabilization of any AE to be followed up as specified in this protocol, whichever comes later.

If a patient decides to discontinue study treatment early, a Premature EOT Visit (see [Section 10.1.3.2](#)) should be scheduled prior to treatment discontinuation, if possible. If not possible, the Premature EOT should be scheduled as soon as possible after treatment discontinuation. In the case of early discontinuation, no sample for measuring plasma concentration should be taken at the Premature EOT Visit, or at any subsequent visits. For patients who discontinue treatment but remain in the study, the remaining study visits should occur as scheduled where possible. The IRT should be notified of EOT.

All cases of permanent treatment discontinuation should be recorded by the Investigator in the appropriate pages of the e-CRF.

#### **10.3.5 Procedure and consequence for patient withdrawal from study**

Patients may withdraw from the study before study completion if they decide to do so, at any time and irrespective of the reason. Withdrawal of consent for treatment should be distinguished from withdrawal of consent for follow-up visits. Patients will be told that they are free to withdraw from the study at any time without any adverse effect on their care; however, if they no longer wish to take the IMP, they will be encouraged to remain in the study and attend the remaining study visits. The value of all their study data collected during their continued involvement will be emphasized as important to the public health value of the study.

If possible, the patients are assessed using the procedure normally planned for the EOS visit.

Patients who withdraw should be explicitly asked about the contribution of possible AEs to their decision to withdraw consent, and any AE information elicited should be documented. Preferably the patient should withdraw consent in writing and, if the patient or the patient's representative refuses or is physically unavailable, the site should document and sign the reason for the patient's failure to withdraw consent in writing.

All confirmed study withdrawals should be recorded by the Investigator in the appropriate screens of the e-CRF and in the patient's medical records. In the medical record, at least the date of the withdrawal and the reason should be documented.

For patients who fail to return to the site, unless the patient withdraws consent for follow-up, the Investigator should make the best effort to contact the patient (eg, contact patient's family or private physician, review available registries or health care databases), and to determine his/her health status, including at least his/her vital status. Attempts (3 phone call attempts followed by a

certified letter) to contact such patients must be documented in the patient's records (eg, times and dates of attempted telephone contact, receipt for sending a registered letter).

Patients who have withdrawn from the study cannot be re-randomized (treated) in the study. Their inclusion and treatment numbers must not be reused.

## **10.4 OBLIGATION OF THE INVESTIGATOR REGARDING SAFETY REPORTING**

### **10.4.1 Definitions of adverse events**

#### **10.4.1.1 Adverse event**

An **AE** is any untoward medical occurrence in a patient or clinical investigation patient administered a pharmaceutical product and which does not necessarily have to have a causal relationship with the study treatment.

#### **10.4.1.2 Serious adverse event**

An **SAE** is any untoward medical occurrence that at any dose:

- Results in death, or
- Is life-threatening, or  
Note: The term "life-threatening" in the definition of "serious" refers to an event in which the patient was at risk of death at the time of the event; it does not refer to an event which hypothetically might have caused death if it were more severe.
- Requires inpatient hospitalization or prolongation of existing hospitalization, or
- Results in persistent or significant disability/incapacity, or
- Is a congenital anomaly/birth defect, or
- Is a medically important event.

Medical and scientific judgment should be exercised in deciding whether expedited reporting is appropriate in other situations, such as important medical events that may not be immediately life-threatening or result in death or hospitalization but may jeopardize the patient or may require medical or surgical intervention (ie, specific measures or corrective treatment) to prevent one of the other outcomes listed in the definition above.

Note: The following list of medically important events is intended to serve as a guideline for determining which condition has to be considered a medically important event. The list is not intended to be exhaustive:

- Intensive treatment in an emergency room or at home for:
  - Allergic bronchospasm

- Blood dyscrasias (ie, agranulocytosis, aplastic anemia, bone marrow aplasia, myelodysplasia, pancytopenia, etc)
- Convulsions (seizures, epilepsy, epileptic fit, absence, etc).
- Development of drug dependence or drug abuse.
- ALT >3 times ULN + total bilirubin >2 times ULN or asymptomatic ALT increase >10 times ULN.
- Suicide attempt or any event suggestive of suicidality.
- Syncope, loss of consciousness (except if documented as a consequence of blood sampling).
- Bullous cutaneous eruptions.
- Cancers diagnosed during the study or aggravated during the study.
- Chronic neurodegenerative diseases (newly diagnosed) or aggravated during the study.

#### **10.4.1.3 Adverse event of special interest**

An AESI is an AE (serious or nonserious) of scientific and medical concern specific to the Sponsor's product or program, for which ongoing monitoring and immediate notification by the Investigator to the Sponsor is required. Such events may require further investigation in order to characterize and understand them. Adverse events of special interest may be added, modified or removed during a study by protocol amendment.

The AESI for this study are:

- Pregnancy of a female patient entered in a study as well as pregnancy occurring in a female partner of a male patient entered in a study with IMP/NIMP:
  - Pregnancy occurring in a female patient included in the clinical trial or in a female partner of a male patient entered in the clinical trial. It will be qualified as an SAE only if it fulfills one of the seriousness criteria (see [Section 10.4.1.2](#))
  - In the event of pregnancy in a female patient, IMP should be discontinued
  - Follow-up of the pregnancy in a female patient or in a female partner of a male patient is mandatory until the outcome has been determined (see [Appendix A](#)).
- Symptomatic overdose (serious or nonserious) with IMP/NIMP
  - A symptomatic overdose (accidental or intentional) with the IMP/NIMP is an event suspected by the Investigator or spontaneously notified by the patient and resulting in clinical symptoms and/or signs accompanied by administration of more than twice the intended daily dose within a 24-hour period. It will be recorded in the e-CRF as an AESI with immediate notification "Symptomatic OVERDOSE (accidental or intentional)" in all cases and will be qualified as an SAE only if it fulfills the SAE criteria

Note that an asymptomatic overdose with the IMP/NIMP, accidental or intentional, defined as administration of more than twice the intended daily dose within a 24-hour period, without clinical symptoms and/or signs, either suspected by the Investigator or spontaneously notified by the patient, not based on accountability assessment. It will be recorded as an AE "Asymptomatic OVERDOSE, accidental or intentional."

- ALT increase >3 times ULN.

